Following TKR, patients receive physical therapy either at home or at a skilled nursing rehabilitation facility and then transition to outpatient rehabilitation for 4-6 weeks.²⁰ The primary objective of therapy is to help the patient regain strength and mobility after surgery by strength and mobility exercises and functional training.²¹ Improved function is reported by 70-80% of patients and decreased pain is reported by 85-90% of patients receiving physical therapy.²² While physical therapists are effective at enhancing function and strength outcomes via rehabilitation exercises following TKR, encouraging patients to engage in the recommended 150 minutes/week of moderate-to-vigorous intensity physical activity during and after therapy is outside of their focus and not typically discussed.¹³

To date, only a few studies have focused on increasing overall physical activity levels in TKR patients; however, the increases in activity observed have been modest compared to changes observed in non-TKR populations and interventions were costly or resource intensive.²³⁻²⁵ Due to the high volume of contact time outpatient physical therapists have with TKR patients (2-3 times/week for 4-6 weeks) and the sense of rapport that is established between the therapist and patient,²¹ physical therapists may be a promising avenue to deliver a physical activity intervention. Given the success of physical therapists to achieve patient strength, mobility, and range of motion goals following TKR, it is likely that they could help patients increase their overall physical activity levels. TKR requires rehabilitation; thus, having physical therapists deliver a physical activity intervention during the required rehabilitation is a novel and efficient approach to reach patients and promote physical activity. *This research is significant because it is the first step towards building a progressive line of research targeting the development of a low-additional cost and translatable physical activity intervention that will have the ability to*

be widely disseminated by physical therapists providing rehabilitation, both in home or outpatient, to TKR patients.

Preliminary Studies:

The PACE study (AHRQ K12HS023011) compared weight loss programs that started either before knee replacement (PACE) or started 12 weeks after surgery (Delayed PACE). Sixteen patients were randomized (63.3±7.5 years old, 69% female, 69% White, BMI of $36.5 \pm 5.1 \text{ kg/m}^2$) to PACE or Delayed PACE. Primary outcomes from 11 participants were objectively assessed at 26 weeks after surgery. Nine participants provided self-reported outcomes at approximately 12.78±1.5 months after knee replacement. Participants in Delayed PACE lost significantly more weight (-7.6±5.9kg, -7.9±5.9%) than PACE (-2.5±2.7kg, -2.6±2.6%) at 26 weeks ($P=0.03$). Delayed PACE maintained greater weight loss outcomes than participants in PACE at one year post-operatively. Pain intensity decreased ($P<0.001$) and function improved ($P=0.001$) significantly, but no significant changes were observed in physical activity (Table 1).

Table 1. Physical Activity Pre- and Post-Surgery in PACE (n=6) & Delayed PACE (n=7)

	Baseline	12 Weeks	26 Weeks
Bouted MVPA, min/week			
PACE	81.2±141.8	3.5±5.4	33.3±76.4
Delayed PACE	37.6±85.7	62.1±135.8	78.1±108.0
Steps/day			
PACE	5715.7±3098.0	4255.6±1687.8	4991.8±2910.2
Delayed PACE	6062.4±2817.6	4943.6±1653.2	6324.4±2201.3

The research team has experience with recruitment of TKR patients in the Columbia, SC area. Currently, we have recruited 12 patients who underwent a TKR to participate in an ongoing study examining the use of Fitbits and social support on physical activity over a 4-month period. To date, 73% of patients recruited for this study are from the Columbia, SC region. Additionally, across the 5 orthopedic surgeons within the Palmetto Health USC Orthopedic Center, an average of 21.8 TKR are completed each week.

3) Objectives / Research Aims

The purpose of this proposed project is to conduct a pilot randomized controlled trial to examine the feasibility and preliminary efficacy of a physical therapist led physical activity intervention on physical activity levels in TKR patients after surgery. The specific aims of the project are:

Aim 1: To examine the feasibility and acceptability of conducting a randomized controlled trial examining a physical therapist led physical activity intervention for TKR patients within an outpatient physical therapy facility. Specifically, enrollment, retention, session attendance and duration, treatment fidelity, and patient and physical therapist satisfaction will be examined.

Aim 2: To examine the effect of a physical therapist led physical activity intervention on the changes in physical activity, physical function, and pain in TKR patients.

4) Setting

The study procedures will be performed at Palmetto Health USC Orthopedic Centers. Potential patients will be identified and recruited after they attend their first physical therapy appointment by physical therapists participating in the study. Patients who are interested in participating will complete the informed consent process with the Principal Investigator or study research assistants. Study data and consent forms will be stored in a locked office at Palmetto Health USC Orthopedic Centers and the University of South Carolina Technology Center to Promote Healthy Lifestyles.

5) Resources Available

The purpose of this study is to examine the feasibility of conducting a physical therapist led physical activity intervention in a clinical setting. We will strive to recruit a total of 50 patients. If recruitment efforts are slow, we will plan to recruit additional physical therapists to participate in the study and assist with recruitment over the 15 month granted funded period of time.

[name], the Principal Investigator and Assistant Professor in the Department of Exercise Science at USC, will oversee all study related procedures, included but not limited to recruitment, behavioral intervention, and data collection and analysis. [name] has extensive experience overseeing behavioral clinical trials.

[name], Co-Investigator and Senior Physical Therapist, will help recruit patients at Palmetto Health USC Orthopedic Centers and will coach participants as part of the intervention during standard physical therapy appointments.

[name], Co-Investigator and Clinical Psychologist, will serve as the mentor to [name] as well as oversee delivery and treatment fidelity of the behavioral intervention. Additionally, [name] serves as a PI for another study through Palmetto Health (Pro00033131 Promoting Health in Pregnancy and Postpartum).

All members of the study team will have a copy of the study protocol and know their respective research duties.

6) Prior Approvals

NA

7) Study Design

a. Recruitment Methods

Patients will be recruited from Palmetto Health USC Orthopedic Center. After completing the first outpatient physical therapy appointment, potentially eligible patients

identified by Palmetto Health Physical Therapists will be provided information about the study verbally by a USC research staff member. Interested patients will be able to ask questions and read the consent form. They will have the opportunity to complete the informed consent process either at the first or second outpatient physical therapy appointment.

b. Inclusion and Exclusion Criteria

After initial identification of potential patient participants by physical therapists, research staff will screen patients for eligibility criteria in-person or over the telephone.

Inclusion criteria:

Eligible participants will 1) be 40-79 years of age, 2) have had a knee replacement in the last 2 months, 3) be willing to wear an accelerometer for 7 days during assessments, and 4) be English speaking.

Exclusion criteria:

As all patients will be under physicians' supervision post-TKR, participants will only be excluded if they (1) have any contraindications to activity, (2) have a mobility limiting comorbidity (e.g. spinal stenosis), or (3) have a scheduled surgery (i.e., TKR on contralateral knee) within the next 6 months.

c. Local Number of Subjects

We will aim to randomize 50 patients that had a knee replacement within the last 2 months and are attending outpatient physical therapy at the Palmetto Health USC Orthopedic Center. We anticipate that we will need to approach and screen approximately 75 patients to enroll our goal of 50 patients.

d. Study-Wide Number of Subjects

NA

e. Study Timelines

Subject participation will last 12 weeks. We estimate it will take 15 months to complete the study, which will include finished study enrollment, data collection and data analysis (See Figure 1).

Figure 1. Project Timeline

	Project Month														
	1	2	3	4	5	6	7	8	9	10	11	12	13	14	15
Finalize protocol & IRB approval	X	X	X												
Recruit TKA patients (n=50)				X	X	X	X	X	X	X	X	X	X		
Intervention				X	X	X	X	X	X	X	X	X	X		
Completing 12 week assessments				X	X	X	X	X	X	X	X	X	X	X	
Data Analysis														X	X
Prepare manuscript & presentations														X	X
Draft & submit NIH R21 or R01														X	X

f. Study Endpoints

[figure not shown]
Assessments will be completed before the second outpatient therapy session (baseline) and at 12 weeks after TKR. Detailed descriptions and a timeline of outcomes are provided below in the text and Table 2. Briefly, at both assessments, participants will be asked to complete surveys (demographics, brief medical history, KOOS, PROMIS, self-identification), which should take approximately 20 minutes to complete. Based on participant preferences, surveys will be able to be completed on paper or online via RedCAP, with the exception of the PROMIS surveys which are computer adaptive surveys. Participants will also be given an Actigraph Link accelerometer and ActivPAL monitor to wear for 7 days at each assessment. These monitors will be provided at the in-person assessment or mailed to the participants. At the end of the 7 days, these monitors will be returned to the PT clinic or participants will be provided with a prepaid padded envelope to return the monitor. Only at 12 weeks will participants complete functional tests and the Surgery and Medication Questionnaire, which will take approximately 15 minutes to complete. In the event participants are unable to complete the function tests at the in-person assessment, we will ask participants to complete the chair stand test at home and self-report the outcomes. Participants will not be asked to complete the 6-minute walk or timed up and go at home. Participants will receive \$20 for completing the 12-week assessment.

Measure	Baseline	12 Weeks
Participant Demographics	X	
Participant height and weight	X	X
Brief Medical History	X	X
Knee Injury and Osteoarthritis Outcome Score (KOOS)	X	X
PROMIS Pain Intensity, Pain Interference, & Mobility	X	X
WOMAC Pain and Stiffness	X	X
Physical Function		
6-minute walk		X
Timed up and go		X
Chair stands		X
Physical activity (Actigraph)	X	X
Sedentary time (ActivPAL)	X	X
Self-Reported Exercise Identity	X	X
PATH Study Survey		X

Primary Outcomes: The feasibility and acceptability of conducting a randomized controlled trial within an outpatient physical therapy setting is the primary endpoint. Specifically, we will examine the number of participants enrolled vs. approached, participant retention, number of therapy sessions attended, session duration, and treatment fidelity. Further, participants will complete a PATH Study Survey at the 12 week assessment. Physical therapists will complete a brief evaluation about delivering the PATH program.

Secondary Outcomes:

- Physical activity will be measured using Actigraph Link accelerometers owned by the TecHealth Center at the University of South Carolina. During assessments, participants will be asked to wear the Actigraph on their waist for 7 days. Non-wear time will be defined as ≥ 90 minutes with zero activity counts, allowing for up to 2 minutes of <100 counts/min.²⁶ Physical activity will be categorized as light (100-2019 counts/min) and moderate-to-vigorous (MVPA) (≥ 2020 counts/min).²⁷ Total MVPA over the week will be calculated. Steps/day will also be obtained. A valid day will be considered if participants wore the accelerometer for at least 10 hours/day. Participants will also be asked to complete a log indicating times the accelerometer was worn and taken off over the 7-day assessment period.
- Sedentary time will be measured using ActivPAL™ (PAL Technologies Ltd, Glasgow, UK), a small lightweight (15 g) uni-axial accelerometer. The time spent sitting/lying, standing, and walking, transitions and step counts will be determined. The ActivPAL summarizes data in 15 second intervals over 24 hours at a sampling frequency of 10 Hz.²⁸ During assessments, participants will be asked to wear the ActivPAL on their thigh for 7 days. Participants will also be asked to complete a log indicating times the ActivPAL was worn and taken off over the 7-day assessment period.
- Physical function measures will include the chair stand, timed up and go, and 6-minute walk test. All physical function tests will be completed following Osteoarthritis Research Society International (OARSI) recommendation procedures.²⁹ During the chair stand test, patients are asked to complete as many chair stand repetitions as possible during a 30-second period. The Timed Up and Go Test assesses the time in seconds taken to rise from a chair, walk 3-meters, turn, walk back to the chair, and sit down. The Six Minute Walk Test evaluates the maximal distance a patient can cover during a 6-minute period.
- Patient-Reported Outcomes will be assessed using two methods: 1) Patient-Reported Outcomes Measurement Information System (PROMIS)³⁰ utilizes a computer adaptive test via RedCap.³¹ We will assess pain intensity, pain interference, and mobility; 2) Western Ontario and McMaster Universities Arthritis Index (WOMAC) is a 15-item survey assessing pain and stiffness over the last 48-hour on a 5-point Likert scale.³²
- Self-reported exercise identity will be assessed at baseline and 12-week assessments using the Self-Reported Exercise Identity Scale.³³ Participants will rate on a scale from 1 (strongly disagree) to 5 (strongly agree) their feelings relating to exercise identity. Examples include, “I would feel a real loss if I were forced to give up exercising” and “I need exercise to feel good about myself.”

g. Procedures Involved

Design Overview: We propose to conduct a pilot two-arm cluster randomized controlled trial with patients attending outpatient physical therapy following TKR. The proposed project was developed in collaboration with [name], Senior Physical Therapist at Palmetto Health USC Orthopedic Center. Over 9 months, TKR patients (n=50) attending outpatient physical therapy at Palmetto Health USC Orthopedic Center will be recruited and randomized to either 1) PATH-12 (control), or 2) PATH. Due to potential contamination of the intervention between patients in PATH-12 and PATH during typical open, group-like physical therapy settings, we have opted to randomize physical therapy sites instead of individual patients. Specifically, physical therapy sites will be randomized to either Immediate or Delayed. The first phase of the study will take place starting in November and end after 25 participants have been recruited. During this time, those sites randomized to Immediate will receive the PATH intervention and those sites randomized to Delayed will receive the PATH-12 intervention. There will then be a “wash out period” to allow for all the participants to finish their current PT. After this “wash out period”, the second phase of the study will begin and will end after 25 participants have been recruited. During this time, those sites randomized to Immediate will receive the PATH-12 intervention and those sites randomized to Delayed will receive the PATH intervention.”

Screening: Participants will be required to complete a brief screening after the first physical therapy appointment. Research staff will administer the screening in-person or over the telephone. The screening will assess eligibility criteria and willingness to participate. Following the completion of the screener, eligible and interested participants will be invited to complete the informed consent process.

Randomized Conditions:

PATH-12 (control). Patients randomized to receive PATH-12 will undergo the standard physical therapy following TKR. The study will not change any treatment patients typically receive and instead will just document how long sessions occur and if any aerobic activity goals were set. In addition to the standard physical therapy received and to enhance retention in the study, all participants who receive PATH-12 will be given a brief physical activity coaching session led by a trained USC research staff member at 12 weeks following the completion of the assessment. Participants will receive all materials

provided to PATH and the session is expected to last approximately 1 hour. In the event this cannot be completed in-person, it will be completed over the telephone.

PATH. Patients randomized to receive PATH will undergo the standard physical therapy following TKR. In addition, physical therapists will briefly discuss lifestyle and moderate-to-vigorous physical intensity activity at each session. At least once/week, physical therapists will help patients set a SMART (Specific, measurable, attainable, realistic, timely) goal related to overall aerobic physical activity and identify strategies that will help them achieve their goal. Physical therapists will use motivational interviewing techniques and check in on patients' progress towards goals at each session. Physical therapists will be encouraged to engage in physical activity coaching and goal setting during down time while patients are completing aerobic warm up, rehabilitation exercises, or during ice, manual therapy, neuromuscular electrical stimulation, or scar management to ensure these discussions do not add additional time to the regular therapy session.

Intervention Data Collection. Physical therapists for both randomized conditions will document the session start and end times as well as any goals that are set during the sessions. Physical therapists can document the session information on a paper form

Treatment Fidelity. Due to the open, group-like nature of physical therapy and patient confidentiality, we are unable to audio record treatment sessions. Therefore, to monitor treatment fidelity to ensure intended session content for both conditions is delivered and that unintended session content (i.e., contamination such as goal setting on physical activity levels with a patient randomized to PATH-12) is not delivered, physical therapists will complete a session checklist. In addition, random observations will occur by USC research staff. The physical therapist and observation fidelity checklists will monitor session duration, goals set, and indication if aerobic physical activity was discussed.

h. Data and Specimen Banking

NA

i. Statistical Analysis

Descriptive statistics will be used to describe baseline characteristics, establish recruitment and retention rates, and examine intervention intensity (session frequency, duration, and fidelity) and patient and therapist satisfaction. Mixed ANOVA or ANCOVAs, if appropriate adjustments are required based on baseline characteristics, will examine the changes in physical activity levels (MVPA/week, steps/day), and pain (PROMIS and WOMAC) across time between PATH and PATH-12. Additionally, differences between PATH and PATH-12 in physical function (chair stands, Timed Up and Go, 6-minute walk) will be examined at 12 weeks. Although the proposed study may not be powered to detect significant differences, the results will allow us to collect feasibility and acceptability data, refine the intervention, if necessary, and determine effect sizes for future grant submissions.

j. Data Management

All surveys will be administered either on paper or online via REDCap (secure, web application for building and managing online surveys and databases – managed by the University of South Carolina). Paper surveys will be stored in a locked filing cabinet at Palmetto Health-USC Orthopedic Center or the TecHealth Center at University of South Carolina. All computer files will be password protected. Only the study team will have access to the data.

k. Confidentiality

A number will be assigned to the participant who agrees to be a part of the study. This number will be used on the project records rather than their name, and no one other than the study team will be able to link the data with the name. Study records/data will be stored in locked filing cabinets and protected computer files at Palmetto Health USC Orthopedic Center and the University of South Carolina's TecHealth Center.

l. Provisions to Monitor the Data to Ensure the Safety of Subjects

Patient enrollment numbers, consent documents, the data collection sheet and any reportable events will be monitored by the Study Coordinator every month.

Any issues found will be rectified as appropriate and preventative actions, as needed, will be taken in efforts to eliminate the issue in the future.

m. Withdrawal of Subjects

Participants will be informed they can leave the research at any time without penalty. If a participant decides to withdraw, no more information will be collected. The participants will be made aware of this during the consent process.

Any data collected during their participation may be used by the investigators for the purposes described above. Choosing not to be in the study will not result in any penalty or loss of benefit to which participants are entitled. Specifically, the choice not to be in this study will not negatively affect a participant's right to any present or future medical treatment or his/her present or future employment.

8) Risks to Subjects

The risks of participating in this study are minimal. Participants may experience:

1. Feelings of muscle soreness and fatigue during physical function tests or engaging in physical activity. Although participants will be experiencing muscle soreness and fatigue from the surgery, we will attempt to minimize any additional symptoms. Participants will be allowed to take breaks at any time during function

tests and the physical activity goals will be tailored specifically based on the participants progress after surgery. The physical therapist will work with the participant to ensure a safe and reasonable goal is set to minimize additional symptoms following surgery. Participants will be encouraged to stop engaging in physical activity immediately if at any time they are injured or are encouraged to stop engaging in physical activity from their physical therapist/physician/medical professional.

2. Skin irritation from wearing the physical activity monitors. Participants will be asked to wear two physical activity monitors, one on their waist, and one on their thigh for 7 days. The waist-worn monitor will only be worn during waking hours to minimize discomfort. The ActivPAL will be securely taped with water proof sealing on the participants thigh and be worn 24 hours for 7 days. In the event the participant experiences discomfort, the participant will be asked to remove the tape. Participants will be provided with additional tape and asked to reapply the monitor once the skin irritation resolves.

9) Potential Benefits to Subjects

Participants may or may not experience any benefits from participating in this study. If participants modify activity behaviors, they may experience positive changes to health and mood. Additionally, this research will help us understand if a physical therapist led physical activity intervention can help to increase activity after knee replacement.

10) Provisions to Protect the Privacy Interests of Subjects

The research study will be explained to potential subjects in a private manner. Consenting will be done also in a private room, away from other subjects or Palmetto staff. Participants will have the option to not answer any question that they do not feel comfortable answering.

11) Compensation for Research-Related Injury

NA

12) Economic Burden to Subjects

NA

13) Consent Process

Informed consent will be obtained either after the first outpatient physical therapy appointment or before the second appointment by a USC research team member. Full details of the study will be discussed, and participants will be reminded that participation is voluntary. Disclosure will be made of the nature and potential risks of participating and all participants will be asked if they have any questions about their

participation to ensure they understand the procedures. We estimate it will take approximately 15 minutes to complete the consent process. The paper consent form has been developed according to the requirements of Palmetto Health and the University of South Carolina Institutional Review Boards. Additionally, the consent process with each participant will be documented on the informed consent checklist. A copy of all signed IRB-approved consent forms will be provided to the participant.

14) Process to Document Consent in Writing

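### Therapists who know their site's current arm decide which patients are put forward, so PATH and PATH-12 patients can differ through selection, and the feasibility count starts after that choice

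*Combined protocol and SAP*

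**What the plan says.** **Allocation.** Section 7g (Design Overview) states: "we have opted to randomize physical therapy sites instead of individual patients". For the first phase: "During this time, those sites randomized to Immediate will receive the PATH intervention and those sites randomized to Delayed will receive the PATH-12 intervention". After a wash-out the arms swap, and "those sites randomized to Immediate will receive the PATH-12 intervention and those sites randomized to Delayed will receive the PATH intervention". Each phase runs until 25 participants have been recruited.

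**Identification.** Section 4 says: "Potential patients will be identified and recruited after they attend their first physical therapy appointment by physical therapists participating in the study". Section 7a says that potentially eligible patients "identified by Palmetto Health Physical Therapists will be provided information about the study verbally by a USC research staff member". Section 7b gives the order: "After initial identification of potential patient participants by physical therapists, research staff will screen patients for eligibility criteria in-person or over the telephone". Section 5 says that the co-investigator who is a senior physical therapist "will help recruit patients at Palmetto Health USC Orthopedic Centers and will coach participants as part of the intervention".

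**Delivery.** In PATH, according to Section 7g, "physical therapists will briefly discuss lifestyle and moderate-to-vigorous physical intensity activity at each session". Under Treatment Fidelity, therapists in both conditions complete checklists, partly to show that activity goal-setting has not reached PATH-12 patients.

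**Analysis and endpoints.** Section 7i compares change over time in activity and pain by mixed ANOVA, or by ANCOVA if baseline characteristics call for adjustment. Physical function is compared at 12 weeks only. Section 7f makes feasibility the primary endpoint, including the number enrolled against the number approached.

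**The concern.** In a cluster trial, randomising sites protects the comparison of patients only if the way patients enter does not depend on the site's arm. Here the arm is in force before any patient in the phase is identified, and the people who identify patients are those whose workload and task change with it. A therapist who is about to coach may, without intending to, put forward patients who seem likely to take to coaching, and be less particular in a PATH-12 phase.

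Two things are at stake. One is Aim 2, whose effect sizes are meant to support later grant applications: a selection difference between arms would be read as a treatment effect. The other is the primary feasibility result, because an enrolment proportion counted from those approached says nothing about patients whom therapists did not put forward.

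**Working it through.** The plan states no power, significance level, effect size or derivation of 50, so there is no figure to reproduce. The check is a tracing of the sequence, followed by illustrations.

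**1. Order of events.** Site arm fixed for the phase (7g); patient attends first appointment (4, 7a); therapist identifies (4, 7a, 7b); research staff inform, screen and consent (4, 7a, 7b). Allocation precedes identification in both phases.

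**2. Do therapists know the arm?** The documents do not say so in words. It follows from their role: they coach at each session in PATH, must not set activity goals in PATH-12, and record both.

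**3. Is there a later safeguard?** Staff screening checks eligibility among patients already put forward. The documents describe no consecutive identification, no recruiter masked to phase, and no record of eligible patients not put forward. One exclusion, a comorbidity that limits mobility, is defined only by an example and leaves room for judgement.

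**4. Room for selection.** Section 7c expects about 75 approached for 50 enrolled: 50/75 = 66.7%. The Preliminary Studies text gives 21.8 TKRs a week. Over the 9 months in 7g (39.1 weeks) that is 21.8 x 39.1 = about 853; over the 10 months marked in Figure 1 (43.5 weeks), about 948. So 75 is 75/853 = 8.8% or 75/948 = 7.9% of operations. The pool is an upper bound: the share who are eligible and attend these sites is not given.

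**5. What each analysis removes.** Let g0 and g12 be the gaps between arms at baseline and at 12 weeks that selection alone would produce.
- Mixed ANOVA, group by time: bias = g12 - g0. A stable gap (g12 = g0) cancels. Selection of patients who would recover faster (g12 > g0) does not.
- ANCOVA with slope b on baseline: bias = g12 - b x g0.
- Chair stands, timed up and go, 6-minute walk: no baseline value, so bias = g12 in full unless other covariates absorb it. Section 7i names none.

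**6. Illustration of scale (assumed inputs).** Suppose therapists in PATH phases leave out the lowest fraction q on a normally distributed prognostic factor that correlates r with the outcome, and leave out no one in PATH-12 phases. The shift is r x phi(z_q)/(1 - q), where phi is the normal density and z_q the q-quantile.

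| q | shift in factor (SD) | shift in outcome (SD), r = 0.3 / 0.5 / 0.7 |
|---|---|---|
| 0.1 | 0.19 | 0.06 / 0.10 / 0.14 |
| 0.2 | 0.35 | 0.10 / 0.17 / 0.24 |
| 0.3 | 0.50 | 0.15 / 0.25 / 0.35 |

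Now take a gap of d SD left in the analysed variable, no treatment effect, and a two-sided 5% t-test. The noncentrality is d x sqrt(n/2).

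| d (SD) | rejection, 25 per arm | rejection, 20 per arm |
|---|---|---|
| 0.2 | 10.7% | 9.5% |
| 0.3 | 18.0% | 15.2% |
| 0.5 | 41.0% | 33.8% |

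Both columns ignore clustering, which would change them. Equal arms are also assumed: the plan fixes 25 per phase, not per arm.

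**The case against.** The strongest reply is that the plan already limits the problem. Every site delivers both conditions in turn, so fixed differences between sites cancel. Activity and pain are analysed as change, so a stable baseline gap drops out. Exercise identity is measured at baseline and bears on motivation, alongside pain, mobility and monitor data. Research staff apply the eligibility criteria. No passage invites therapists to choose by motivation. The study is a pilot whose primary endpoint is feasibility, and it concedes limited power. With 25 per arm the standard error of a difference is sqrt(2/25) = 0.28 SD (clustering ignored), so a modest bias would be lost in the noise.

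Much of this stands. It would be wrong to say that site randomisation gives no protection, or that motivation is wholly unmeasured. What remains is selection on expected recovery or responsiveness, which neither the crossover nor a change score removes, and the function tests, which have no baseline. Exercise identity is a partial proxy and is not named as a covariate. Imprecision does not cancel bias; it makes bias harder to see in the effect sizes carried forward. The pilot label does not dispose of the point either, because the recruitment process is among the things this pilot is meant to test.

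A reader might also infer that Sections 4 and 7a contradict each other on who recruits. That is mostly loose wording: both have therapists identifying patients and research staff completing consent. It needs aligning, no more.

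**Conclusion.** The concern holds as a design weakness that should be put right: arm-aware selection is possible, nothing in the plan would prevent or reveal it, and the primary enrolment count begins after it. The one inferred link is that therapists know the arm, and their delivery role makes that unavoidable.

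The size of any bias cannot be derived from the documents. A reader might be tempted to put a figure on it, for instance by assuming a selection gap of 0.2-0.4 SD and baseline reliability of 0.5-0.7, which gives 0.2 x 0.3 = 0.06 to 0.4 x 0.5 = 0.20 SD. The documents supply neither input. The formula suits only the ANCOVA variant, not the mixed ANOVA of change, and says nothing about the function tests. The documents also state no expected effect against which such a figure could be called large. Nor do they show that therapists will select; they show only that they could.

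The exposure is greatest for the three function tests, smaller for activity and pain, and separate again for the feasibility count, which is affected whether or not selection differs by arm.

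**What to change.** In Sections 4 and 7a:

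- Have the research staff who already inform, screen and consent patients identify every post-TKR first visit at participating sites from the appointment lists, and approach these patients consecutively in both phases. If list access is not permitted, have therapists refer every such patient without discretion.
- Use one recruitment script in both phases that does not reveal the site's current arm before consent and the baseline surveys. This cannot extend to the 7-day monitor wear, which overlaps coaching given at each session.
- Keep a log by site and phase of patients seen, eligible, approached and consented, and compare it between arms. The log also gives the enrolment endpoint a denominator that starts before therapist choice.
- Align the two sections on who identifies patients, who makes first contact and who consents.

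Cost: a little more staff time, and permission for research staff to view appointment lists before consent, which the documents do not currently describe. The design, sample size and intervention stay as they are. The log should start with recruitment, since it cannot be rebuilt reliably afterwards.
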